| DMDSAT | DMD Functional Ability Self-Assessment Tool |
| ECG | electrocardiogram |
| eCRF | electronic case report form |
| EMA | European Medicines Agency |
| EQ-5D | EuroQoL 5-Dimension |
| EQ-VAS | EuroQoL visual analogue scale |
| ET | early termination |
| FVC | forced vital capacity |
| HRQL | health-related quality of life |
| IRT | interactive response technology |
| ITT | intention-to-treat |
| LoA | loss of ambulation |
| MAR | missing at random |
| MCMC | Markov Chain Monte Carlo |
| MedDRA | Medical Dictionary for Regulatory Activities |
| MEP | maximum expiratory pressure |
| MHRA | Medicines and Healthcare products Regulatory Agency |
| MI | multiple imputation |
| MIP | maximum inspiratory pressure |
| mITT | modified intention-to-treat |
| MMRM | mixed model for repeated measures |
| MNAR | missing not at random |
| MRI | magnetic resonance imaging |
| MRS | magnetic resonance spectroscopy |
| NSAA | North Star Ambulatory Assessment |
| PK | pharmacokinetic |
| PP | per-protocol |
| PT | preferred term |
| PROM | Patient-Reported Outcome Measure |
| PUL | Performance of Upper Limb |
| rNSAA | revised North Star Ambulatory Assessment total score |
| SAE | serious adverse event |
| SAP | statistical analysis plan |
| SOC | system organ class |
| TEAE | treatment-emergent adverse event |
| TESAE | treatment-emergent serious adverse event |
| UN | unstructured covariance matrix |

| Abbreviation or Specialist Term | Explanation |
|---------------------------------|---|
| WHODD | World Health Organization Drug Dictionary |

1. OVERVIEW

This statistical analysis plan (SAP) details the statistical methods to be used in the analyses and presentation of the data collected during the **double-blind treatment period** in Study PTC124-GD-041-DMD, also referred to as Study 041, for **EMA/MHRA**. The statistical methods to be used for the data collected during the entire study including open-label treatment period will be described in a separate SAP.

This document is prepared on the basis of the final study protocol version 4.0 (dated 21JUL2020). The reader is referred to the study protocol, the electronic case report form (eCRF), general eCRF completion guidelines, and various data collection instruments employed in the study for details of study design, conduct and data collection.

This SAP is to be reviewed and approved prior to the first study database lock. There will be 2 database locks for this study. The first database lock (soft lock) will occur when all subjects completed the 72-week double-blind treatment. The final database lock will occur when all subjects have completed 72-week open-label treatment period.

2. STUDY OVERVIEW

2.1. Study Design

Study 041 is a Phase 3, international, multicenter, randomized, double-blind, parallel, placebo-controlled, efficacy and safety study of ataluren in subjects with nonsense mutation Duchenne muscular dystrophy (DMD) and its open-label extension.

This study will enroll subjects ≥ 5 years old. Subjects who fulfill all the inclusion/exclusion criteria will be randomized in a 1:1 ratio to placebo or ataluren.

Treatment will comprise continuous daily administration of double-blind ataluren or placebo for 72 weeks, followed by open-label ataluren for another 72 weeks. Throughout the study, study drug should be taken three times per day - the 1st dose (10 mg/kg) in the morning, the 2nd dose (10 mg/kg) at mid-day, and the 3rd dose (20 mg/kg) in the evening.

Visits will be performed every 12 weeks during the double-blind treatment period and every 24 weeks during the open-label extension. Visit windows are ± 7 days. The Baseline and Week 72 visits consist of 2 consecutive days. Subjects that discontinue from the study early will complete an early termination (ET) visit. All subjects will have a follow-up phone visit 4 weeks (± 7 days) after the last dose of study drug.

The primary analysis will be targeted on the subset of subjects who are 7 to 16 years old with 6-minute walk distance (6MWD) ≥ 300 meters and time to stand from supine ≥ 5 seconds at baseline. In subjects who are 5 and 6 years old, a treatment benefit may be obscured due to the confounding effect of normal growth and development. Therefore, subjects who are 5 and 6 years old are eligible for the study but will not be included in the primary analysis. Subjects who are ≥ 17 years old and ambulatory at baseline may be considered to have a milder phenotype and a slower trajectory of disease progression. To limit the variability of study results, these subjects will not be included in the primary analysis population.

2.2. Study Objectives

2.2.1. Primary Objective

The primary objective of this study is to determine the effect of ataluren on ambulation and endurance as assessed by the 6-minute walk test (6MWT).

2.2.2. Secondary Objectives

The secondary objectives of this study are to:

- Determine the effects of ataluren on ambulation and burst activity as assessed by timed function tests
- Determine the effects of ataluren on lower-limb muscle function as assessed by the North Star Ambulatory Assessment (NSAA)
- Assess the safety profile of ataluren
- Evaluate the correlation between plasma concentration of ataluren and functional outcomes

- Evaluate the plasma pharmacokinetic (PK) profile of ataluren

2.2.3. Exploratory Objectives

The exploratory objectives of this study are to:

- Determine the effects of ataluren on upper-limb muscle function strength as assessed by the Performance of Upper Limb (PUL) and by the DMD Upper Limb Patient-Reported Outcome Measure (PROM) (in subjects ≥ 7 years old at baseline)
- Determine the effects of ataluren on muscle strength as assessed by myometry (in subjects < 7 years old at baseline)
- Determine the effects of ataluren on skeletal muscle integrity as assessed by magnetic resonance imaging (MRI) (at pre-qualified sites only)
- Determine the effects of ataluren on subject- and parent/caregiver-reported health -related quality of life (HRQL) as assessed by at-home questionnaire
- Determine the effects of ataluren on pulmonary function as assessed by forced vital capacity (FVC)

2.3. Study Endpoints for Double-Blind Treatment Period

2.3.1. Primary Endpoint

The primary endpoint is slope of change in 6MWD over 72 weeks.

2.3.2. Secondary Endpoints

The key secondary endpoints are:

- Slope of composite of average change in times to run/walk 10 meters, climb 4 stairs, and descend 4 stairs over 72 weeks
- Change from baseline to Week 72 in NSAA total score

Other secondary endpoints are:

- Change from baseline to Week 72 in 6MWD
- Composite of average change in times to run/walk 10 meters, climb 4 stairs, and descend 4 stairs at Week 72
- Change from baseline to Week 72 in time to run/walk 10 meters
- Change from baseline to Week 72 in time to climb 4 stairs
- Change from baseline to Week 72 in time to descend 4 stairs
- Time to loss of ambulation (LoA) over 72 weeks
- Time to loss of stair-climbing over 72 weeks
- Time to loss of stair-descending over 72 weeks
- Risk of loss of NSAA items over 72 weeks

- Ataluren safety profile characterized by type, frequency, severity, and relationship to study drug of any adverse events (AEs), or of abnormalities of laboratory tests, vital signs, physical examinations, or electrocardiograms (ECGs)

2.3.3. Exploratory Endpoints

Exploratory endpoints include:

- Changes from baseline to Week 72 in PUL total score and domain subscores (in subjects ≥ 7 years old at baseline)
- Change from baseline to Week 72 in DMD Upper Limb PROM total score and domain subscores (in subjects ≥ 7 years old at baseline)
- Risk of loss of DMD Upper Limb PROM items over 72 weeks (in subjects ≥ 7 years old at baseline)
- Change from baseline to Week 72 in myometry parameters (in subjects < 7 years old at baseline)
- Change from baseline to Week 72 in muscle fat fraction as assessed by MRI (at pre-qualified sites only)
- Changes from baseline to Week 72 in HRQL as assessed by EuroQoL 5-Dimension (EQ-5D)
- Change from baseline to Week 72 in FVC

2.4. Sample Size

The hypothesis of this study is that the slope of change in 6MWD from baseline to Week 72 (end of double-blind treatment period) will be 1.0 meter/week better in the ataluren arm than in the placebo arm, within a subset of subjects who are ≥ 7 to 16 years old with baseline 6MWD ≥ 300 meters and baseline time to stand from supine ≥ 5 seconds. The baseline 6MWD is defined as the maximum of the 6MWDs from a valid 6MWT on Day 1 and Day 2. Similarly, the Week 72 6MWD is defined as the maximum of the 6MWDs from a valid 6MWT on Day 1 and Day 2 of the Week 72 visit (end of double-blind treatment period). With a 1:1 randomization, 154 subjects will be required (77 subjects in the ataluren treatment arm and 77 subjects in the placebo arm) to detect a difference of 1.0 meter per week between ataluren and placebo with 85% power (two-sided $\alpha = 0.05$), assuming a common standard deviation of 2.058 meters per week. Further assuming a premature discontinuation rate of $\sim 5\%$, a total of 162 subjects (81 subjects in the ataluren treatment arm and 81 subjects in the placebo arm) will be enrolled for the primary endpoint analysis. The study is expected to enroll ~ 340 subjects overall, including those outside of the primary analysis population.

2.5. Randomization

Randomization is an accepted means to reduce bias and allows for the highest standard of evidence in documenting a treatment effect. The stratified, block randomization approach will be used. The system will assign the next available randomization number, within the list for the stratum, to the patient. Such a method allows treatment arms to be balanced with respect to the predefined stratification factors as well as for the number of subjects in each arm. The process will be established and performed centrally through an interactive response technology (IRT) system to maximize the integrity and security of the randomization and ensure appropriate access and convenience-of-use by the investigational sites.

In order to balance treatment allocation, the following stratification factors will be used:

- Baseline concomitant corticosteroid type (deflazacort, prednisone/prednisolone)
- Baseline 6MWD (<300 meters, 300 to <350 meters, 350 to <400 meters, ≥ 400 meters) where baseline 6MWD is the maximum of the Day 1 and Day 2 6MWDs
- Baseline time to stand from supine (<5 seconds, ≥ 5 seconds)

2.6. Blinding

Double-blind administration of study treatments during double-blind period is utilized to provide additional and substantial protection against motivational bias on the part of subjects, parents/caregivers, clinic staff, and other study personnel, with respect to assessment of efficacy and safety parameters.

2.7. Study Assessments

2.7.1. 6-Minute Walk Test

The 6MWT will be performed at Screening (Visit 1), baseline (Visit 2, two 6MWTs performed), Week 12 (Visit 3), Week 24 (Visit 4), Week 36 (Visit 5), Week 48 (Visit 6), Week 60 (Visit 7), and Week 72 (Visit 8, two 6MWTs performed) in the double-blind treatment period.

2.7.2. Timed Function Tests

Timed function tests of peak physical capacity, including the times taken to run/walk 10 meters, climb 4 stairs, descend 4 stairs, and stand from supine, will be performed using standardized procedures. These assessments will be performed at Screening (Visit 1), baseline (Visit 2), Week 12 (Visit 3), Week 24 (Visit 4), Week 36 (Visit 5), Week 48 (Visit 6), Week 60 (Visit 7), and Week 72 (Visit 8) in the double-blind treatment period.

The time taken to stand from supine will not be used as an endpoint in this study.

2.7.3. North Star Ambulatory Assessment

The NSAA measures change in physical function by using standardized procedures and consists of 17 activities. The NSAA will be used to evaluate physical function, using standardized procedures. The NSAA will be performed at Screening (Visit 1), baseline (Visit 2), Week 12 (Visit 3), Week 24 (Visit 4), Week 36 (Visit 5), Week 48 (Visit 6), Week 60 (Visit 7), and Week 72 (Visit 8) in the double-blind treatment period.

2.7.4. Myometry

Myometry will be performed only in subjects who are <7 years old at baseline.

Upper and lower extremity myometry will be performed using a myometer following standardized procedures. Muscle groups to be evaluated include knee extensors and elbow flexors. Bilateral assessments should be done, and 3 measurements should be recorded from each muscle group on each side if possible. These parameters will be monitored at baseline (Visit 2), Week 12 (Visit 3), Week 24 (Visit 4), Week 36 (Visit 5), Week 48 (Visit 6), Week 60 (Visit 7), and Week 72 (Visit 8) in the double-blind treatment period.

2.7.5. PUL and DMD Upper Limb PROM

PUL (version 2.0) and DMD Upper Limb PROM will be assessed only in subjects who are ≥ 7 years old at baseline.

PUL is assessed using standard equipment and procedures at baseline (Visit 2), Week 12 (Visit 3), Week 24 (Visit 4), Week 36 (Visit 5), Week 48 (Visit 6), Week 60 (Visit 7), and Week 72 (Visit 8) in the double-blind treatment period.

The DMD Upper Limb PROM questionnaire will be available in all languages relevant for this study and will be completed by the parent/caregiver. If possible, the same parent/caregiver should complete the questionnaire each time. The DMD Upper Limb PROM questionnaire will be completed at baseline (Visit 2), Week 12 (Visit 3), Week 24 (Visit 4), Week 36 (Visit 5), Week 48 (Visit 6), Week 60 (Visit 7), and Week 72 (Visit 8) in the double-blind treatment period.

2.7.6. Magnetic Resonance Imaging (MRI)

MRI and/or magnetic resonance spectroscopy (MRS) will be conducted at a subset of sites that have been qualified by a central imaging vendor to perform this assessment. MRI/MRS data will be analyzed centrally. MRI/MRS will be performed at baseline (Visit 2), Week 24 (Visit 4), Week 48 (Visit 6), and Week 72 (Visit 8) in the double-blind treatment period. The baseline imaging may be performed during the screening period, and post-baseline imaging may be performed ± 4 weeks of visit date.

2.7.7. Spirometry

Spirometric evaluation of FVC and other parameters (eg, maximal inspiratory and expiratory pressures, peak expiratory flow) in the sitting position will be performed at screening (Visit 1), Baseline (Visit 2), and Week 72 (Visit 8) in the double-blind treatment period. If a patient loses ambulation as determined by inability to perform the 10-meter run/walk test within 30 seconds at a clinic visit, then spirometry will be performed at that visit and at all subsequent visits.

2.7.8. HRQL At-Home Questionnaires

HRQL will be measured via the EQ-5D and patient-reported functional ability will be measured using the DMD Self-Assessment Tool (DMDSAT).

These questionnaires will only be completed where validated versions in the local language are available and will be completed by the subject (where possible) and a parent/caregiver.

If possible, the same parent/caregiver should complete the questionnaire each time. The questionnaires will be provided at Visit 1 and completed at home by the subject and a parent/caregiver between Visit 1 and Visit 2 (pre-treatment) and approximately once per month for the rest of the study. Site personnel will assess subject compliance with the questionnaires will be checked at baseline (Visit 2), Week 12 (Visit 3) Week 24 (Visit 4), Week 36 (Visit 5), Week 48 (Visit 6), Week 60 (Visit 7), and Week 72 (Visit 8) in the double-blind treatment period.

2.7.9. Pharmacokinetic (PK)

No PK sample will be collected during double-blind period.

2.7.10. Adverse Events

An AE is any untoward medical occurrence associated with the use of a drug in humans, whether or not it is considered related to the study drug.

All AEs (both serious and nonserious) that occur in subjects during the AE reporting period must be recorded. All AEs are to be recorded in the source documents and on the eCRF using concise medical terminology; whenever possible terms contained in Medical Dictionary for Regulatory Activities (MedDRA) should be employed.

2.7.11. Laboratory Assessment

Hematology, biochemistry, and urinalysis laboratory assessment will be analyzed by the central laboratory. These parameters will be measured at Screening (Visit 1), baseline (Visit 2), Week 24 (Visit 4), Week 48 (Visit 6), and Week 72 (Visit 8) in the double-blind treatment period.

2.7.12. Vital Signs, Height, Weight, and Physical Examination

Vital signs (including systolic and diastolic blood pressure, pulse rate, and body temperature), height, and weight will be monitored at Screening (Visit 1), baseline (Visit 2), Week 12 (Visit 3) Week 24 (Visit 4), Week 36 (Visit 5), Week 48 (Visit 6), Week 60 (Visit 7), and Week 72 (Visit 8) in the double-blind treatment period.

A full physical examination (including evaluation of cardiovascular system, chest and lungs, thyroid, abdomen, nervous system, skin and mucosae, musculoskeletal system, eyes, ears, nose, mouth, throat, spine, lymph nodes, extremities, and genitourinary) will be conducted at Screening (Visit 1), and Week 72 (Visit 8) in the double-blind treatment period.

A symptom-directed physical examination will be conducted at Baseline (Visit 2), Week 24 (Visit 4), and Week 48 (Visit 6) in the double-blind treatment period.

2.7.13. 12-Lead Electrocardiogram (ECG)

A 12-lead ECG will be obtained at Screening (Visit 1), Week 24 (Visit 4), Week 48 (Visit 6), and Week 72 (Visit 8) in double-blind treatment period. The ECG will be performed and interpreted locally. The findings will be captured on the eCRF.

2.7.14. Echocardiogram

Echocardiogram will be obtained at Screening (Visit 1) and Week 72 (Visit 8) in the double-blind treatment period.

3. STUDY POPULATIONS

3.1. Intention-to-Treat Population

The intention-to-treat (ITT) population will include all subjects who are randomized, with treatment assignments designated according to initial randomization, regardless of whether subjects receive a different study treatment from the one randomized. In addition, subjects in this population must have a valid 6MWT at baseline, and at least one valid post-baseline 6MWT. This population will be used for summary and analysis of efficacy endpoints.

3.2. Modified Intention-to-Treat Population

The modified intention-to-treat (mITT) population will include all subjects in the ITT population who meet the following additional criteria: 7 to 16 years old with 6MWD ≥ 300 meters and time to stand from supine ≥ 5 seconds at baseline. This population will be used for the primary and secondary efficacy endpoint analyses, and other supportive efficacy analyses.

3.3. As-Treated Population

The as-treated population consists of all randomized subjects who receive study treatment, with treatment assignments designated according to actual treatment received. This population will be used for summary and analysis of safety endpoints.

3.4. Per-Protocol Population

The per-protocol (PP) population is a subset of the mITT population. Subjects who meet the following criteria will be excluded from the PP population:

- Received study treatment different from the randomized treatment throughout the double-blind period
- Did not have a valid 6MWT at baseline or a valid Visit 8 6MWT within the Study Analysis Visit window for Week 72
- Non-compliance to study drug administration
- Had significant inclusion or exclusion criteria violations
- Had protocol deviations which may impact effectiveness of study treatment

This population will be used for primary efficacy endpoint as supportive efficacy analysis.

A separate document including detailed PP population exclusion criteria and the list of subjects excluded from PP population will be finalized prior to treatment unblinding.

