9.2.4 Per-Protocol Population

This population will include all subjects in the mITT population who meet the following additional criteria: received study treatment in agreement with randomization, completed the 72-week double-blind treatment period, had drug compliance between 75% and 125%, inclusive, and had no inclusion or exclusion criteria violations and no major protocol violations. This population will be used for supportive efficacy analyses.

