6. EFFICACY EVALUATION

Unless otherwise specified, the actual weeks at each visit will be used for all MMRM analyses using all valid assessments. The by-visit summaries will be generated based on the analysis visits described in Section 4.8.

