6.1.2. Primary Analysis

The rate of change in 6MWD over 72 weeks (slope) in the mITT population will be considered as the primary efficacy endpoint.

A MMRM model will be employed using a random intercept and a random slope of change per week using observed data assuming the missing assessments are MAR. The slope will be compared between ataluren and placebo, and the estimated treatment difference with corresponding 95% confidence interval (CI) will be provided. The estimated difference in the change at Week 72 will also be provided to facilitate interpretation. The MMRM model will include baseline concomitant corticosteroid type (deflazacort, prednisone/prednisolone), baseline 6MWD category (<300 meters, 300 to <350 meters, 350 to <400 meters, ≥400 meters), baseline 6MWD, treatment, week (actual week at the visit as a continuous variable), the interaction of week and baseline 6MWD, and the interaction of week and treatment. The unstructured covariance matrix (UN) will be used in the MMRM model. Other types of covariance matrix (heterogenous Toeplitz, Toeplitz, and compound symmetric) will be explored in the case of non-convergence of UN. For this analysis, any subjects who lose ambulation during the study will be assigned a 6MWT result of 0 meters for the first visit in which the subjects lose ambulation and set for missing for all visits afterwards while they participate in the study.

The primary endpoint will be tested at the significance level of 0.05 (two-sided). If $p < 0.05$, then the primary endpoint will be considered statistically significant, and the study will be declared positive.

The example SAS code is listed below:

```
PROC MIXED data=<dataset> method=reml;  
  CLASS Cortico Subjid Trt C6WMD;  
  MODEL N6WMD = Cortico C6WMD Trt B6WMD Week Week*B6WMD  
    Week*TRT/S CL;  
  RANDOM Int Week/type=un subject=Subjid;  
  LSMEANS TRT / pdiff at Week=72 CL;  
RUN;
```

where

N6WMD = 6WMD at each visit (Baseline to Week 72)

B6WMD = Baseline 6WMD
C6WMD = Baseline 6WMD category
Cortico = Baseline concomitant corticosteroid type
Week = Actual study week at each visit
Trt = Treatment group
Subjid = Subject
Int = Intercept

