6.1.3. Supportive/Sensitivity Analyses

6.1.3.1. Analysis of Covariance (ANCOVA) Using Multiple Imputation (MI)

As a sensitivity analysis, an ANCOVA model will be used to evaluate the difference in change in 6MWD from baseline to Week 72 after missing data have been imputed via a pattern mixture model utilizing MI. The estimated treatment difference in change from baseline of 6MWD at Week 72 and the corresponding 95% confidence interval (CI) will be provided. The ANCOVA model will include baseline concomitant corticosteroid type (deflazacort, prednisone/prednisolone), baseline 6WMD category (<300 meters, 300 to <350 meters, 350 to <400 meters, ≥ 400 meters), treatment, as well as baseline 6MWD as a covariate. For this analysis, all 6MWD will be assigned to an analysis visit according to the analysis visit window described in Section 4.8. Any subjects who lose ambulation during the study will be assigned a 6MWT result of 0 meters for the visit in which the subjects lose ambulation and for all remaining visits while they participate in the study. For subjects with missing 6MWD due to other reasons, the missing assessments at post-baseline visits will be imputed using the pattern-mixture model MI assuming the missing values are missing not at random (MNAR) utilizing the complete case missing value pattern (CCMV - subjects who completed primary efficacy assessments without missing values). Detailed imputation method is described in [Appendix 2](#).

The example SAS code is listed below:

```
PROC MIXED data=<dataset> method=reml;  
  CLASS Cortico Trt C6MWD;  
  MODEL CHG6MWD = Cortico C6MWD Trt B6MWD /CL;  
  LSMEANS TRT / pdiff CL;  
RUN;
```

where

CHG6MWD = change from baseline in 6MWD at Week 72
B6MWD = Baseline 6MWD
C6MWD = Baseline 6MWD category
Cortico = Baseline concomitant corticosteroid type
Trt = Treatment group

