6.1.3.2. ITT and PP Populations

As a supportive analysis, the primary MMRM analysis will be repeated using both the ITT and PP populations. In addition, the ANCOVA model after MI will also be repeated for ITT population. The baseline time to stand from supine (<5 seconds, ≥ 5 seconds) will be included in the testing model in the ITT analysis.

6.1.3.3. *Modification of mITT Criteria (+/- 15%)*

As supportive analyses, separate MMRM models similar to the primary analysis will be used to evaluate the change in 6MWD from baseline to Week 72 for all subjects with a baseline 6MWD ≥ 255 meters (ie, -15% from the 6MWD ≥ 300 meter lower bound) or baseline 6MWD ≥ 345 meters (ie, +15% from the 6MWD ≥ 300 meter lower bound)) and who also meet the age and stand from supine criteria for the mITT population (ie, 7 to 16 years old and time to stand from supine ≥ 5 seconds at baseline).

6.1.3.4. *Checking Missing at Random Assumption*

For the primary analysis, an additional sensitivity analysis will be employed to check the MAR assumption underlying the MMRM model where the reason for drop-out is considered. Subjects with following discontinuation reasons will be imputed using MI method using subjects in placebo arm who completed double-blind period of the study without missing values.

- Adverse event
- Withdrew consent
- Investigator decision

This analysis will be performed for mITT population. Detailed method and SAS codes are described in [Appendix 3](#).

6.1.3.5. *Using Average of Day 1 and Day 2 6MWDs Rather than Maximum*

The primary analysis uses the maximum of valid Day 1 and Day 2 6MWDs for baseline and Week 72. As a sensitivity analysis, the same analysis will be repeated with the average of valid Day 1 and Day 2 6MWDs for baseline and Week 72 for mITT population. For this analysis, the actual week for Baseline and Visit 8 will be calculated based on the first day of the visit.

6.1.3.6. *Assess the Impact of COVID19*

To assess the impact of COVID19, a sensitivity analysis will be performed similarly to the primary MMRM analysis and ANCOVA analysis after MI by removing all COVID19 impacted visits (as collected on CRF) for mITT and ITT populations. The baseline time to stand from supine (<5 seconds, ≥ 5 seconds) will be included in the testing model in the ITT analysis.

6.1.3.7. *Assess the Impact from Potential Correlation among Siblings*

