6.2.2.4. Loss of Ambulation (LoA) and Stair Climb/Stair Descend

LoA will be defined as persistent inability to perform the 10-meter run/walk test within 30 seconds at any post-baseline visit and for all remaining visits. Loss of stair-climbing will be defined as persistent inability to perform the 4-stair climb test within 30 seconds at any post-baseline visit and for all remaining visits. Loss of stair-descending will be defined as persistent inability to perform the 4-stair descend test within 30 seconds at any post-baseline visit and for all remaining visits. (Note: All subjects will have the ability to perform these tests within 30 seconds at screening and baseline, per the inclusion criteria.)

Time to LoA will be evaluated using Kaplan-Meier estimation, Log-rank test, and Cox proportional hazards model (assuming similar covariates as the primary efficacy model) in both mITT and ITT populations. Similar analyses will be performed for time to loss of stair-climbing and time to loss of stair-descending.

A separate analysis will evaluate time to LoA in subjects with baseline 6MWD <300 meters in ITT population.

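### Read literally, the SAP's per-protocol rule drops compliant 72-week completers who lost ambulation, so membership depends on the primary outcome

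*SAP*

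**What the plan says.** - **Double-blind SAP 3.4** makes the PP set a subset of mITT and excludes a boy who "Did not have a valid 6MWT at baseline or a valid Visit 8 6MWT within the Study Analysis Visit window for Week 72". None of its bullets mentions LoA. It leaves the detailed criteria and the list of excluded boys to a separate document, to be finalised before unblinding.
- **Protocol 9.2.4** requires that the boy "completed the 72-week double-blind treatment period, had drug compliance between 75% and 125%, inclusive", received the treatment he was randomised to, and had no eligibility or major protocol violations. A Week 72 walk is not a condition.
- **Protocol section 8** wants boys kept in the study after LoA where possible, and 6.2.13 schedules spirometry at every visit from then on. Non-ambulant completers are therefore expected.
- **Double-blind SAP 6.1.2** (primary MMRM) gives a boy with LoA "0 meters for the first visit in which the subjects lose ambulation and set for missing for all visits afterwards". **SAP 6.1.3.1** (ANCOVA after multiple imputation) gives him "0 meters for the visit in which the subjects lose ambulation and for all remaining visits while they participate in the study".
- **Double-blind SAP 6.1.3.2** uses the PP set as support for the primary endpoint: "the primary MMRM analysis will be repeated using both the ITT and PP populations".
- **Double-blind SAP section 8** lists the removal of the evaluable population as a change from the protocol, but not the altered PP definition.

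**The concern.** A PP set should remove boys who departed from the protocol. This criterion can instead remove boys who followed it and had the worst result on the endpoint being analysed. Take a compliant boy who walks at Weeks 12 to 36, loses ambulation at Week 48, stays on study drug and attends Visit 8. He meets Protocol 9.2.4. Having done no walk at Visit 8, he fails SAP 3.4 as written.

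Selection on a post-randomisation outcome matters most when treatment affects that outcome. If one arm has fewer losses of ambulation, that part of its advantage is missing from the PP estimate. Agreement or disagreement between PP and mITT is then hard to interpret, although that comparison is the reason for running the PP analysis.

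**Working it through.** **The plan's own figure.** SAP 2.4 gives a difference of 1.0 m/week, SD 2.058 m/week, two-sided alpha 0.05 and 85% power. Per arm, n = 2 × 2.058² × (1.960 + 1.036)² / 1.0² ≈ 76.1, rounded up to 77, or 154 in total. This matches the SAP; power at 77 per arm is 85.4%. The calculation does not involve the PP rule.

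**Does a boy with LoA have a valid Visit 8 6MWT?** The SAP does not define validity for assigned zeros. Three readings are possible for a boy who no longer performs the walk:

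1. *Valid means a test performed.* He is out of PP whenever he lost ambulation. This fits the use of the word in Protocol 3.2 (criteria 8 and 9), Protocol 4.2 and SAP 4.2, where it describes walks that were done. The LoA zero is described as assigned.
2. *An assigned zero counts, with the 6.1.2 handling.* He is in if LoA first occurs at Visit 8. He is out if it occurred earlier, because later values are set to missing. Membership then depends on when he lost ambulation.
3. *An assigned zero counts, with the 6.1.3.1 handling.* He has 0 m at Week 72 and stays in.

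Readings 1 and 2 make membership depend on the primary outcome. Only reading 3 agrees with Protocol 9.2.4 for these boys.

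**Size, as an illustration on mean Week 72 change.** The documents give no LoA rates, so the inputs below are assumptions: mean baseline B = 360 m (range 300 to 420), mean change W = −40 m among boys still walking in both arms, and LoA boys at 0 m (change −B). The LoA shares are p for placebo and a for ataluren.

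Difference with LoA boys kept = [a(−B) + (1 − a)W] − [p(−B) + (1 − p)W] = (p − a)(B + W).

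Difference with LoA boys removed = W − W = 0.

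| LoA placebo vs ataluren | Part lost from PP, B = 360 | Range, B = 300 to 420 | Per week (÷ 72), B = 360 |
|---|---|---|---|
| 5% vs 2.5% | 0.025 × 320 = 8.0 m | 6.5 to 9.5 m | 0.11 m/week |
| 10% vs 5% | 0.05 × 320 = 16.0 m | 13 to 19 m | 0.22 m/week |
| 20% vs 10% | 0.10 × 320 = 32.0 m | 26 to 38 m | 0.44 m/week |
| 10% vs 10% | 0 m | 0 m | 0 m/week |

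For scale, the design difference is 1.0 × 72 = 72 m. The mITT estimates in Table 1 of the changes-from-planned-analysis document run from 8.26 to 9.95 m.

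**Precision.** With effect and SD unchanged, removing 5%, 10%, 15% or 20% of 77 per arm lowers power from 85.4% to 83.6%, 81.6%, 79.4% or 76.9%. This is secondary to the shift in the estimate.

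**The case against.** A reader might infer that the SAP definitely removes every boy with LoA and so deletes any benefit that comes through preserved walking. The documents do not support that, for four reasons:

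- No section says that an assigned 0 m is not valid. SAP section 6 says "the actual weeks at each visit will be used for all MMRM analyses using all valid assessments", yet the assigned zero still enters the model. The set-to-missing rule in 6.1.2 handles data for one analysis and does not define validity.
- LoA rests on a different test: "LoA will be defined as persistent inability to perform the 10-meter run/walk test within 30 seconds at any post-baseline visit". Some boys with LoA may still perform a 6MWT and stay in PP.
- The separate PP document may already contain an exception.
- The illustration uses mean change at Week 72, whereas PP repeats the slope model with a single zero. The two middle-to-large scenarios give 16 and 32 m, more than any reported mITT estimate. LoA may also be uncommon here: mITT excludes boys below 300 m, whom Protocol 11.2.4 regards as at high risk of early loss of ambulation.

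All of this stands and limits how firmly the exclusion and its size can be stated.

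The consequence is also limited. PP is supportive and lies outside the testing sequence in SAP 4.6. The boy in the example stays in mITT and ITT with his zero, and time to LoA is analysed separately in both. The changes document moves primary interest to ITT and does not list PP among its 6MWD sensitivity analyses.

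Two cautions apply to any fix. The Visit 8 walk is the only listed stand-in for completing 72 weeks, so an LoA exception without an explicit completion criterion could let early dropouts into PP. Treatment differences have also been reported, so any change to membership is now post hoc.

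None of this removes the mismatch with Protocol 9.2.4, its absence from SAP section 8, or a bullet whose natural reading selects on the endpoint.

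**Conclusion.** The point holds in a limited form. Followed literally, SAP 3.4 excludes compliant completers with no Visit 8 walk because of LoA, whom the protocol would keep. That ties PP membership to the primary outcome, and the departure is undeclared. Whether it happened depends on how assigned zeros were classified and on a document not available here.

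The size is unknown. Under the assumptions above (baseline 360 m, equal change among walkers, LoA from 5% vs 2.5% up to 20% vs 10%) the PP estimate would lose 8 to 32 m of mean Week 72 change, and nothing if LoA rates are equal. The low end is about the size of the reported mITT difference. These figures show what could be lost and do not estimate what the slope model lost. The mITT and ITT results are not affected. The point is worth correcting because PP is a named supportive analysis of the primary endpoint.

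**What to change.** - **Double-blind SAP 3.4:** replace the bullet with three alternatives: *no valid baseline 6MWT; or 72-week double-blind period not completed; or period completed but no valid Visit 8 6MWT in the Week 72 window, for a reason other than loss of ambulation as defined in 6.2.2.4.*
- **Handling:** completers with LoA stay in PP with the 6.1.2 handling used in the mITT primary MMRM.
- **Consistency:** carry the same wording into the PP exclusion document, and list the departure from Protocol 9.2.4 in SAP section 8.
- **Transparency:** because treatment results are already known, make the change as a dated addendum, report PP under both definitions, and give the number excluded for LoA by arm.

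No new data are needed, since LoA is already derived for the time-to-event analysis. The cost is one short addendum and one extra supportive run, labelled post hoc.
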